### 7.12.3 Vital Signs

Vital signs data and their change from baseline will be summarized descriptively in tables by treatment and analysis visit.

All vital sign data will be listed.

### 7.12.4 ECGs

ECG parameter values and changes from baseline will be summarized descriptively by treatment and analysis visit.

For ECGs, number and percentage of subjects meeting the criteria listed below will be presented in tables:

- Baseline QTc  $< 450$  msec and  $> 500$  msec at EOT
- Baseline QTc  $< 450$  msec and  $500 \text{ msec} \geq \text{QTc} > 480$  msec at EOT
- Baseline QTc  $< 450$  msec and  $480 \text{ msec} \geq \text{QTc} > 450$  msec at EOT
- Change from baseline at EOT in QTc  $> 30$  msec
- Change from baseline at EOT in QTc  $> 60$  msec

These criteria will be applied to both QTcB and QTcF.

Shift tables will present the changes in clinically relevant categories from baseline to EOT. The categories are Normal, Abnormal-not-clinically significant and Abnormal-clinically significant.

All ECG parameters and findings will be listed.

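### The absolute QTc rows count only subjects with baseline below 450 msec, so new crossings of 480 or 500 msec from a higher baseline are not counted by arm

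*SAP*

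**What the plan says.** SAP 7.12.4 states that for ECGs the "number and percentage of subjects meeting the criteria listed below will be presented in tables". Five criteria follow.

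- Row 1: "Baseline QTc $< 450$ msec and $> 500$ msec at EOT"
- Row 2: "Baseline QTc $< 450$ msec and $500 \text{ msec} \geq \text{QTc} > 480$ msec at EOT"
- Row 3: "Baseline QTc $< 450$ msec and $480 \text{ msec} \geq \text{QTc} > 450$ msec at EOT"
- Row 4: "Change from baseline at EOT in QTc $> 30$ msec"
- Row 5: "Change from baseline at EOT in QTc $> 60$ msec"

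The section adds: "These criteria will be applied to both QTcB and QTcF". Rows 1 to 3 concern the absolute EOT value and share one baseline condition. Rows 4 and 5 concern change and have no baseline condition.

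The same section also plans descriptive summaries of ECG values by treatment and visit, a baseline-to-EOT shift table and a full listing. Of the shift table it says: "The categories are Normal, Abnormal-not-clinically significant and Abnormal-clinically significant".

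SAP 5.3 sets the default percentage denominator as all subjects in the treatment group and analysis set. SAP 7.12.4 names no other. Protocol 2.2.4 schedules the 12-lead ECG at baseline and EOT only.

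**The concern.** A baseline cut-off of 450 msec suits a row for new values above 450 msec. It does not suit rows for values above 480 or 500 msec, because a subject can start between 450 and 480, or between 480 and 500, and still cross the higher limit on treatment. Those crossings fall outside rows 1 and 2. The subjects affected start closest to the limits.

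What is at stake is how the table reads. An arm could show zero in the above-500 row while one of its subjects had an EOT QTc of 510 msec. The change rows recover that subject only if the rise exceeds 30 msec. The laboratory thresholds in SAP 7.12.2 (ALT/AST, bilirubin, creatinine, ALP) carry no baseline condition, and the SAP gives no reason for treating QTc differently.

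**Working it through.** The plan states no figure to reproduce here. The check is on the logic of the five criteria.

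**Criteria**, with b = baseline QTc and e = EOT QTc, in msec (SAP 7.12.4):

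- R1: b < 450 and e > 500
- R2: b < 450 and 480 < e ≤ 500
- R3: b < 450 and 450 < e ≤ 480
- R4: e − b > 30
- R5: e − b > 60

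**Example subjects**

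| b | e | e − b | Rows entered |
|---|---|---|---|
| 449 | 505 | 56 | R1, R4 |
| 450 | 505 | 55 | R4 only |
| 450 | 511 | 61 | R4, R5 |
| 455 | 510 | 55 | R4 only |
| 475 | 505 | 30 | none |
| 485 | 510 | 25 | none |

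A difference of 1 msec at baseline (449 against 450, both ending at 505) decides whether the subject appears in the above-500 row.

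**Where all five rows fail for an EOT value above 500.** The subject must have b ≥ 450, e > 500 and e − b ≤ 30. The last two give b > 470. On an integer grid of b = 450 to 500 (51 values) and e = 501 to 560 (60 values) there are 51 × 60 = 3060 combinations. None enters R1 to R3. For each b from 471 to 500, the values of e from 501 to b + 30 enter no row, which is b − 470 values. The total is 1 + 2 + … + 30 = 465 of 3060. These counts describe the rule and are not estimates of how often it would happen.

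**How many subjects could be affected.** The documents give no rate of baseline QTc ≥ 450 msec. With 102 subjects planned (Protocol 4.1), assumed rates give:

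| Assumed rate | Expected of 102 | Expected of 34 per arm |
|---|---|---|
| 1% | 1.0 | 0.3 |
| 2% | 2.0 | 0.7 |
| 5% | 5.1 | 1.7 |
| 10% | 10.2 | 3.4 |

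Only those who also cross 480 or 500 msec would be miscounted, so the number missed would be smaller.

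**Effect on percentages.** One missed subject turns 1/34 = 2.9% into 0/34 = 0%. The denominator matters less: at the assumed 5%, one counted subject is 1/34 = 2.9% of the arm, against 1/(34 − 1.7) = 3.1% of those who could enter the row.

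**The case against.** The strongest reply is that the rows are not wrong. They are clearly labelled counts of elevations arising from a baseline below 450 msec, which is a coherent question in a placebo-controlled trial. They do not claim to count every high value. Protocol 10.2.3 promises only descriptive ECG summaries, so the SAP already goes beyond it and there is no contradiction. This stands: what is missing is a complementary row. It does not rescue the 480 and 500 msec rows as counts of new crossings, because 455 to 510 is new at both limits and is still left out.

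A second reply is that the information is not lost. SAP 5.3 includes the maximum in descriptive summaries, so an EOT value above 500 msec shows there whatever the baseline. The shift table has no QTc restriction, all ECG data are listed, and Protocol 6.9.3 requires clinically significant abnormalities to be reported as adverse events. With 34 subjects per arm, such a value would be hard to overlook. This also stands. A reader might infer that the plan would conceal a QTc above 500 msec; the documents do not support that. None of these outputs gives a count by arm, however. The maximum shows that at least one subject was high but not how many, and the shift table uses investigator interpretation rather than msec bands.

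Third, a reader might infer that subjects with baseline QTc of 450 msec or more will be enrolled, since no visible criterion in Protocol 4.4 names QTc or ECG. That goes too far. Exclusion criterion 22 is redacted and cannot be checked, and criterion 11 lets the investigator exclude clinically significant disease. The documents leave the question open.

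**Conclusion.** The gap follows directly from the wording of SAP 7.12.4. A subject starting at 450 msec or more who newly crosses 480 or 500 msec is in no absolute row. If the rise is 30 msec or less, the subject is in none of the five rows. Because no other denominator is specified, such subjects remain in the percentages by default.

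Its practical size is unknown. It depends on whether such subjects can enrol, which the redaction leaves unsettled, and on how many there are, for which the 1% to 10% range is an assumption. If criterion 22 excluded them, the gap would have no effect.

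This is a minor safety-reporting improvement. It has no bearing on the primary analysis, and the affected subjects' ECG data are still reported elsewhere.

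**What to change.** In SAP 7.12.4, for both QTcB and QTcF:

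- Add rows for EOT QTc above 450, above 480 and above 500 msec regardless of baseline. That is 3 thresholds × 2 corrections = 6 rows.
- Define any row for new elevations by a baseline at or below that row's own threshold (450, 480 or 500 msec). Use the subjects at risk, meaning those meeting that baseline condition, as its denominator.
- Keep the two change rows.

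With this, 455 to 510 counts as new above 480 and new above 500. A subject going from 485 to 510 counts as new above 500 only. Both enter all three unconditional rows.

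The cost is six table rows and revised definitions for the existing absolute rows. The ECG data are already collected, and study conduct does not change.

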### 7.12.5 Physical Examinations

Physical examination data will be summarized descriptively (number and percentage of the subjects) in tables by treatment and analysis visit.

All physical examination data will be listed.

### 7.12.6 Nevi appearance

Nevi appearance will be summarized descriptively (number and percentage of the subjects) in tables by treatment and analysis visit for subjects' suspicious nevi found:

- Any suspicious nevi found during assessment (Y,N)
- Any clinically significant findings (Y,N).

Nevi appearance data will be listed.

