6.9.4 Nevi Evaluation

Nevi will be assessed at the times shown in the time and events schedule (Table 5.1-1). Baseline nevi evaluation will be conducted at any time during the screening period before randomization. Nevi evaluation at Visit 9 will be performed based on the opinion of the Investigator or a dermatologist or other qualified site staff.

Nevi will be assessed locally by a visual full body examination performed by a dermatologist or other qualified site staff. Any subject with suspicious nevi of clinical concern will have treatment temporarily discontinued and be referred for further nevi evaluation (e.g., biopsy), as deemed necessary by the dermatologist or other qualified site staff. If there are any clinically significant adverse findings from the further nevi evaluation, subjects will not be allowed to continue taking study medication. The results will be recorded in the source documents and the eCRF.

Nevi assessment details will be fully described in a separate document.

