Vital signs and 12-lead ECG variables and changes from baseline will be descriptively summarized at each visit by treatment.

The baseline for the vital sign parameters and 12-lead ECG measurements will be the last valid assessment obtained on Day 1 prior to the administration of double-blind treatment period.

Physical examination and Nevi evaluation

For physical examination, the frequency and percentage of subjects with abnormal physical examinations will be summarized at each time point by body system and treatment.

Nevi assessment will be summarized in table by treatment with frequency and percentage for subjects' suspicious nevi found.

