**Table 5 Analysis Visit Windows for the non-diary data**

Analysis visit	Nominal day	Window
Screening	Day -14	By Day -14
Day 1	First dose day	NA
Week 1	Day 8	Day 3 to 11
Week 2	Day 15	Day 12 to 22
Week 4	Day 29	Day 23 to 42
Week 8	Day 57	Day 43 to 71
Week 12	Day 85	Day 72 to 99
Week 16	Day 113	Day 100 to 134
Week 22 (FU)	Day 155	NA
End of treatment (EOT)	Week 16 study visit or study early termination visit	

The analysis visits are derived according to the following criteria:

- The unscheduled visits are not used for the deriving.
- If a study visit is the only one in an analysis visit window, this study visit becomes the derived analysis visit.
- If there are multiple visits in an analysis visit window, the closest visit to the nominal day becomes the analysis visit. In the event that two visits are the closest visits to the nominal day and equally distanced to the nominal day, the visit after the nominal day becomes the derived visit.
- The follow-up visit will not be derived. The study visit will be used.

- Unscheduled visits and retests (same visit number assigned), will not be displayed in by-visit summary tables, but will be included in the data listings.
- The deriving analysis visit is not applicable to the data not depending on study visit, for example, the AE data.

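### The SAP's only nevi summary table is by analysis visit and omits unscheduled examinations, so it cannot show how many subjects per arm ever had a suspicious nevus

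*SAP*

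**What the plan says.** Nevi appearance is a safety endpoint (protocol 2.2.4, SAP 2.4.6). Post-baseline examinations are scheduled at Week 8, at Week 16 or early termination, and at Week 22, where the examination depends on the examiner's judgement (protocol 6.9.4 and the footnotes to Table 5.1-1).

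- **Protocol 10.2.3:** "Nevi assessment will be summarized in table by treatment with frequency and percentage for subjects' suspicious nevi found". No visit is named. The preceding sentence, on physical examination, does name one: abnormal findings "will be summarized at each time point by body system and treatment".
- **SAP 7.12.6:** "Nevi appearance will be summarized descriptively (number and percentage of the subjects) in tables by treatment and analysis visit". Two yes/no items are tabulated: any suspicious nevus, and any clinically significant finding. The section ends: "Nevi appearance data will be listed".
- **SAP 5.4.4:** "Unscheduled visits and retests (same visit number assigned), will not be displayed in by-visit summary tables". The same sentence goes on to keep them in the data listings. Table 5 also has an EOT analysis visit, which is either the Week 16 visit or the early-termination visit.
- **Protocol 6.9.4:** "Any subject with suspicious nevi of clinical concern will have treatment temporarily discontinued and be referred for further nevi evaluation".
- **SAP section 8:** declares no change from the protocol's statistical analyses.

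**The concern.** A reader of the safety results will want to know how many subjects in each arm developed a nevus of concern. The planned table gives the number positive at each visit, which is a different quantity. A finding at Week 8 leads to a treatment hold and referral, so it need not be recorded again at Week 16. The rows may therefore contain the same subjects, different subjects or a mixture, and the table does not say which.

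A nevus noticed between scheduled visits is the kind of finding that protocol 5.3.5 would route to an unscheduled visit for safety reasons, and the table leaves those visits out. Protocol 1.5 reports that, after multiple dosing in Phase I, the most frequent adverse events were skin-related and included new, darkening and enlarging nevi. A per-subject incidence by dose is thus a natural summary to expect. What is at stake is the clarity of one safety endpoint. No efficacy result depends on it.

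**Working it through.** The documents give no nevi figure to reproduce. The check has two parts: a comparison of the texts, and a bound on what by-visit counts can reveal.

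**1. Comparison of texts**

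| Source | Stratified by | Any-time row | Unscheduled visits |
|---|---|---|---|
| Protocol 10.2.3, physical examination | treatment, body system, time point | not stated | not stated |
| Protocol 10.2.3, nevi | treatment | implied by the absence of a visit, not stated | not stated |
| SAP 7.12.6, nevi table | treatment, analysis visit | none | excluded through 5.4.4 |
| SAP 7.12.6, nevi listing | not a summary | not applicable | included through 5.4.4 |
| SAP 7.12.2, out-of-range laboratory values | treatment | yes, by its wording | not stated |

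The last row shows that the SAP already uses a per-subject count by treatment elsewhere in its safety section.

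**2. What by-visit counts determine**

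Inputs: n = 34 per arm (protocol 4.1); scheduled post-baseline examinations at Weeks 8, 16 and 22. The by-visit counts c₈, c₁₆ and c₂₂ are assumed, because the documents give none. The illustration also assumes that no positive finding appears only at an early-termination visit.

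If N is the number of subjects positive at one or more scheduled visits, then

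max(c₈, c₁₆, c₂₂) ≤ N ≤ min(34, c₈ + c₁₆ + c₂₂).

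The lower end applies when the same subjects recur at each visit. The upper end applies when no subject recurs.

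| Assumed counts (Weeks 8/16/22) | By-visit percentages | Range of N | Range as % of 34 |
|---|---|---|---|
| 1/1/1 | 2.9, 2.9, 2.9 | 1 to 3 | 2.9 to 8.8 |
| 2/2/1 | 5.9, 5.9, 2.9 | 2 to 5 | 5.9 to 14.7 |
| 3/3/2 | 8.8, 8.8, 5.9 | 3 to 8 | 8.8 to 23.5 |

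For 2/2/1: 2/34 = 5.9% and (2 + 2 + 1)/34 = 5/34 = 14.7%.

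**3. Adding unscheduled visits**

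Let u be the number of subjects found only at an unscheduled visit. They are absent from every by-visit row, so u is added to both ends of the range. For 2/2/1:

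- u = 1: 3 to 6 subjects, 3/34 = 8.8% to 6/34 = 17.6%.
- u = 2: 4 to 7 subjects, 4/34 = 11.8% to 7/34 = 20.6%.

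The table would look the same in all of these cases.

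**4. Does the EOT row close the gap?**

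Only in part. It keeps early-termination findings, but it is a single time point. A subject positive at Week 8 and clear at Week 16 is negative at EOT.

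**The case against.** The strongest case on the other side is that this is a presentational matter and that the information is already in planned output.

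- **Listings.** All nevi data are listed, unscheduled visits included. A reader might infer from the table that the number affected is nowhere available. That is wrong, because it can be derived from the listings. It would, however, have to be counted by hand for each arm.
- **Adverse-event tables.** SAP 7.12.1 counts a subject once per preferred term whatever the visit, and Phase I nevus changes were reported as adverse events. This helps but does not settle the matter. Protocol 6.9.4 does not say that a suspicious nevus is to be reported as an adverse event, whereas 6.9.2, 6.9.3 and 6.9.5.2 say so for clinically significant vital-sign, ECG and laboratory abnormalities. The SAP plans a dedicated grouping for hepatic events and none for nevi.
- **Early termination.** A reader might infer that findings leading to withdrawal are lost, or that nothing found before the Visit 6 window opens on Day 50 can enter the table. The documents do not support either. Early-termination examinations have the EOT row, and Table 5 assigns Days 43 to 71 to Week 8.
- **Direction of error.** It is tempting to say that the rows hold different subjects and that the table must understate incidence. Protocol 6.9.4 makes biopsy a matter of judgement and does not say that a nevus ceases to be suspicious. The Visit 9 examination is meant to check whether changes seen on treatment have reversed, which implies following the same nevus. The 14.7% is an upper end under assumed counts, not an estimate.
- **Protocol wording.** The protocol does not use the word cumulative. Its section 10 is the basis for the SAP, so adding a visit dimension can be read as detail. This is a fair point. The per-subject reading rests on the missing visit term and the contrast with the sentence before it.
- **Importance.** The risk-benefit statement (protocol 3.3) does not name nevi, and the only adverse events of special interest defined are hepatic. Darkened or new nevi are also not the same as suspicious ones. This limits the weight of the point.

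What survives is narrow: the table has no any-time row, it omits unscheduled findings, and neither alternative output reliably supplies the missing count.

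**Conclusion.** The point holds as a reporting gap in a descriptive safety table. Followed as written, SAP 7.12.6 with 5.4.4 yields no tabulated number of subjects per arm ever found with a suspicious nevus or a clinically significant finding. The size of the ambiguity depends on the counts observed. In the 2/2/1 illustration the same table fits incidences that differ by a factor of 2.5 (5/2), and unscheduled findings could raise the true figure further without changing the table. This rests on two things: the assumed counts, and a reading of protocol 10.2.3 that is natural but not explicit. The documents do not show that the table will understate incidence, only that it cannot exclude this. The change is worth making because it is nearly free. It has no bearing on the primary analysis.

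**What to change.** Add two rows to the SAP 7.12.6 table, shown for each MT-7117 dose, pooled MT-7117 and placebo:

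1. Subjects with any post-baseline suspicious nevus.
2. Subjects with any post-baseline clinically significant finding.

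Count each subject once, using every scheduled, early-termination and unscheduled evaluation. Take as denominator the subjects with at least one post-baseline evaluation. State in the section that the unscheduled-visit rule of SAP 5.4.4 does not apply to these rows. Footnote how many subjects were found at scheduled and how many only at unscheduled examinations, because unscheduled examinations are prompted by concern and may differ in frequency between arms. Keep the by-visit rows as supportive. If the sponsor intends a by-visit table only, SAP section 8 should say so.

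Cost: two table rows and a footnote. Protocol 5.3.5 already requires unscheduled assessments to be recorded in the eCRF, so no new data or examinations are needed.

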### 7.12.7 Other Safety Assessments

As post hoc analysis, the data collected in the questionnaires for exit interview and PGIC\_2 at follow up visit will be presented in data listing. The summary tables will be generated if the available data is enough.

### 7.13 Pharmacokinetics Assessment

Plasma MT-7117 data will be listed for each subject and scheduled visit and treatment period with the same precision as provided by the bioanalytical laboratory. PK sample collection times, most recent dosing times, as well as derived actual sampling time relative to the most recent dose will be provided in a listing. The actual sampling time relative to the most recent dose will be calculated in hours and rounded to 2 DP. Plots of individual concentration vs actual sampling time will be presented overlaid with treatment in different symbols for each treatment by visit, or overlaid with visits.

The analysis plan for the PPKPD will be in a separate document. and the results will be separately reported.

### 7.14 Exploratory endpoint

Porphyrin and protoporphyrin levels will be listed and summarized by treatment using descriptive statistics. The summary of other exploratory endpoints in Section 2.10 will be presented in a separate report.

### 7.15 Statistical/Analytical issues

#### 7.15.1 The Sunrise and Sunset Time to Use

The primary and some secondary efficacy endpoints are derived from the diary data where sunshine exposure time between 1 hour post sunrise and 1 hour pre-sunset are used. For the subjects exposed to sunlight within the US, the sunrise and sunset time of the fifty states are used. For the subjects expose to sunlight outside of the US, the sunrise and sunset time of corresponding country or areas are used.

The source data of sunrise and sunset time is from the website of the United States Naval Observatory (USNO) Astronomical Applications Department. The accurate sunrise and sunset times for each US state and territory (*or arbitrary non-US location*) on each day in 2018 and 2019 will be used ([http://aa.usno.navy.mil/data/docs/RS\\_OneYear.php](http://aa.usno.navy.mil/data/docs/RS_OneYear.php)).

The fifty US States' sunrise and sunset time are available from the time the subjects' enrolled. With the study going on, the subjects' geographical locations for sunlight exposure will be checked from time to time. The sunrise and sunset time for the countries, cities, and areas will be added into SDTM as needed. The last time new sunrise and sunset time will be added is 5 weeks before the last subject last visit in the study. In the event that any subjects had sun exposure outside of US after that; the time 6:00 and 18:00 will be used as sunrise and sunset time. This is a close approximation of the average sunrise and sunset time for the current accumulated study data in the US.

### **7.15.2 Data Handling of eDiary records**

- (1) If a record has “-0:00” as start/end time, the time will be treated as missing.
- (2) If there is inconsistency between start date and end date of a record for prodromal symptom, the following handling rule will be adapted.
  - If recorded end date is later than start date, the record will be divided per day.
  - If recorded start date is later than end date, the record will not be used for analysis.
- (3) If there are duplicated eDiary records, a record with the latest record time will be used.

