6.7 Efficacy Assessments

6.7.1 Primary Efficacy Endpoint

6.7.1.1 Sunlight Exposure Diary

The sunlight exposure diary will be completed on a daily basis from Screening to the follow-up visit by the subjects. An example of the sunlight exposure diary (extract) is presented in Section 14.3 (Appendix 3).

Subjects will record their sunlight exposure time in the sunlight exposure diary. For each sunlight exposure, they will record the presence, duration (onset time of the first symptom and recovery time) and severity of the prodromal symptoms. Pain, its severity and duration (onset time and recovery time) will also be recorded separately in the dedicated part of the diary. The severity of prodromal symptoms and pain will be measured using an 11-point Likert scale ranging from 0 to 10, with 0 indicating no symptom and 10 indicating greatest severity of symptom.

Subjects will be instructed to recognize the following photo-provoked symptoms as prodromal:

- Burning/hotness/heating up
- Tingling
- Itching/scratchy
- Stinging
- Others

Subject responses in the sunlight exposure diary will be used to investigate the primary

efficacy endpoint. The data from the diary will also be used for the secondary and other efficacy assessments.

Further details will be provided in a separate study reference manual, and statistical assessment methods for this study endpoint are described in Section 10.2.2.1.

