## 5.4 Derived variables and data convention

### 5.4.1 Derived variables for diary data

For this study, only the sunlight exposure between 1 hour post sunrise and 1 hour pre-sunset is considered and collected. The following wording is not repeated.

The subjects will record in their diaries for the sunlight exposure periods (start/end time), prodromal symptom periods, and pain periods. The subjects' sunlight exposure start and end times will be compared with their state capital cities sunrise and sunset times. The sunlight exposure time beyond the interval (from 1 hour post sunrise to 1 hour pre-sunset) will be excluded from the analyses unless it is specified in a different way.

The analysis windows are defined in the table below. The nominal day for each week relative to the first dose day will be used. Day1 is the first dose day.

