#### 5.4.1.1 The average daily time to first prodromal symptom associated with exposure to sunlight

The following is the procedure to calculate the average daily time to first prodromal symptom associated with exposure to sunlight.

1. If the sunlight exposure time is beyond the interval (from 1 hour post sunrise to 1 hour pre-sunset), then this time is excluded by comparing the sunrise/sunset time.
2. The time to first prodromal symptom associated with exposure to sunlight in a day is calculated. It is the sum of the sunlight exposure time before the first prodromal symptom occurred in the day. If a subject had sunlight exposure but no prodromal

symptom in a day, the sum of the sunlight exposure time for the day is used as the sunlight exposure time to the first prodromal symptom.

3. A diary day is qualified if the subject had non-zero duration of sunlight exposure in the day.
4. The average daily sunlight exposure time to the first prodromal symptom at a time point (Baseline, Week 2, 4, 6, 8, 10, 12, 14, 16, and 22) is the average of the sunlight exposure time to the first prodromal symptom of qualified days in the corresponding 14-day window. At least 1 day diary data is required for each 14 day window to be qualified for this calculation.
5. The minute is used as the unit for calculation of the duration. The Duration will not be rounded. However, in data presentation for listings, the duration will be rounded to integer. HH:MM can be used when the duration is more than 60 minutes. For tables, the duration will be rounded to integer for minimum and maximum and to one decimal place for mean, SD, median and confidence intervals.

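### Applied literally, the rule that divides overnight symptom records makes the next day score 0 minutes on the primary endpoint, even when the symptom resolved before that day's exposure

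*SAP*

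**What the plan says.** Protocol 6.7.1.1 has subjects report symptoms separately for each exposure: "they will record the presence, duration (onset time of the first symptom and recovery time) and severity of the prodromal symptoms". A symptom record therefore has its own onset and recovery time and belongs to a particular exposure.

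SAP 7.15.2, rule (2), covers records whose two dates differ: "If there is inconsistency between start date and end date of a record for prodromal symptom, the following handling rule will be adapted". Where the end date is the later one, the instruction is: "If recorded end date is later than start date, the record will be divided per day". The rule gives the later piece no start time. It does not say which exposure that piece is linked to, or whether it can be a first symptom.

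SAP 5.4.1.1 derives the daily value of the primary endpoint. Step 2 says: "It is the sum of the sunlight exposure time before the first prodromal symptom occurred in the day". The same step credits all of a day's exposure only when the subject went outside and the day contains no symptom at all. Step 3 says: "A diary day is qualified if the subject had non-zero duration of sunlight exposure in the day". Step 4 averages the qualified days of the 14-day window and adds: "At least 1 day diary data is required for each 14 day window to be qualified for this calculation".

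The daylight filter in SAP 5.4.1 is worded for exposure only: "The sunlight exposure time beyond the interval (from 1 hour post sunrise to 1 hour pre-sunset) will be excluded from the analyses".

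**The concern.** Dividing a record per day suits endpoints that deduct symptom time overlapping exposure. It does not suit an endpoint that measures time to onset. The later piece continues the previous day's reaction and is not a new onset.

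If that piece counts as a symptom of the later day, its natural start is midnight. No daylight exposure precedes midnight, so the day scores 0. The daylight filter does not remove the piece, because it acts on exposure time. The full-exposure branch does not clearly apply either, because it asks whether the day had a symptom, not whether a symptom began that day. Step 3 then keeps the 0 in the average. A record spanning several dates would leave a piece on each later date.

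The primary endpoint would then mix time to onset with the length of the previous day's reaction. Two programmers working from the same SAP could also derive different primary values from the same diary.

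**Working it through.** The plan states no figure on this point, so there is none to reproduce. The check applies SAP 5.4.1.1 steps 2 to 4 to a constructed case under two readings.

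**Inputs.** The rules come from SAP 7.15.2(2), 5.4.1.1 and 5.4.1.2. The clock times, the 60 minutes of daily exposure and the carry-over shares are assumptions.

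**Case.** A symptom starts on Day 1 at 17:30 and runs past midnight. Day 2 exposure is 10:00 to 11:00, which is 60 minutes. Reading A counts the divided piece as a symptom at 0:00 on Day 2. Reading B counts only symptoms with onset on Day 2.

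| Day 2 situation | 5.4.1.1, reading A | 5.4.1.1, reading B | 5.4.1.2 (exposure minus overlap) |
|---|---|---|---|
| Carried-over symptom ends 02:00, no new symptom | 0 | 60 | 60 − 0 = 60 |
| Carried-over symptom ends 02:00, new symptom at 10:40 | 0 | 40 | 40 if the new symptom lasts to 11:00 |
| Carried-over symptom lasts to 12:00, no new onset | 0 | 60 | 60 − 60 = 0 |

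In the first row, reading A conflicts with 5.4.1.2 for the same day (0 against 60). In the third row the conflict reverses: a bare onset rule credits 60 minutes although the subject had symptoms throughout the exposure. Reading A is therefore clearly wrong only where the carried-over symptom ended before exposure began.

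**Effect on one window.** Suppose each of q qualified days has 60 symptom-free minutes, and k of them score 0 through carry-over. The window mean is 60 × (q − k)/q. For k = 1:

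- q = 14: 60 × 13/14 = 55.7
- q = 7: 60 × 6/7 = 51.4
- q = 3: 60 × 2/3 = 40.0
- q = 1 (the SAP minimum): 0

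**Effect on the treatment difference at Week 16.** Let E be the daily exposure, equal in both arms, and let p be the share of qualified days that score 0 through carry-over. The artificial difference, active minus placebo, is E(1 − p_active) − E(1 − p_placebo) = E(p_placebo − p_active). With assumed shares of 10% on placebo and 5% on active:

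- E = 30: 30 × 0.05 = 1.5 minutes
- E = 60: 60 × 0.05 = 3.0 minutes
- E = 120: 120 × 0.05 = 6.0 minutes

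Equal shares add 0. Reversing the shares reverses the sign.

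**The case against.** The strongest reply is that the SAP never gives the later piece a midnight onset and never says that it feeds step 2. Other text favours an onset-based reading. The endpoint is defined through symptoms tied to daylight exposure (SAP 2.1). The diary records onset per exposure (Protocol 6.7.1.1). The missing-date rules in SAP 7.15.3 assume that each symptom record is linked to an exposure record. On that view, a continuation belongs to the earlier day's exposure. This is fair as a statement of intent. However, the linkage appears only in the missing-date rules. The steps that compute the primary value contain no onset or linkage condition, and nothing exempts a divided piece.

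The reply also limits the scope, and this part stands:

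- A missing end date cannot create a carry-over, because SAP 7.15.3 caps it no later than 23:59 on the day of the linked exposure.
- Under the default sunset of 18:00 in SAP 7.15.1, counted exposure closes at 17:00. A symptom that began by then must last about 7 hours to reach midnight, or less where sunset is later.
- The same derivation applies at baseline, so a stable carry-over rate would partly cancel in the change from baseline.
- SAP 7.1 allows handling rules to be added at the blinded data review. That gives a route to clarify the point but does not itself settle it.

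A reader might also infer that the rule favours the drug. The documents do not support a direction. Shorter reactions on active would give placebo more zeros, but longer exposure on active could produce more overnight reactions there. A reader might further infer that divided pieces inflate the count of symptomatic episodes. That does not follow: the unit of that secondary endpoint is the exposure episode, and nothing in the SAP turns a continuation piece into a further exposure.

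**Conclusion.** The point holds in a limited form. Followed literally, SAP 7.15.2(2) and 5.4.1.1 steps 2 and 3 give 0 minutes for a day that follows an overnight symptom, while 5.4.1.2 credits that day's exposure in full if the symptom had already resolved. It would go too far to say that the SAP mandates the 0, since the endpoint definition points the other way. The defect is that the operative steps permit the 0 and do not apply the definition.

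The error is clear only for carried-over symptoms that ended before the next day's exposure. If the symptom is still present when exposure starts, 0 may be a fair score. In the assumed example, one affected day costs 4.3 minutes of a 60-minute mean with 14 qualified days (60 − 55.7), and more when fewer days qualify. The overall size and direction are unknown, because the documents give no frequency of overnight symptoms. This should be corrected before lock, but it does not rank among the must-fix points. Confidence is medium.

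**What to change.** Before database lock, amend the SAP as follows:

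- In 5.4.1.1 step 2, define the day's first symptom by the original, undivided onset datetime of a symptom linked to an exposure on that day.
- In 7.15.2(2), state that divided pieces are used only to deduct symptom time in 5.4.1.2 and 5.4.1.3 and to derive symptom duration.
- Flag days on which a carried-over symptom is still present when exposure starts, state how they are scored in the main analysis, and show the primary result with and without them.

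The rule can be adopted at the blinded data review under SAP 7.1. It needs no new data. The cost is a few sentences, a small change to the derivation program and one extra sensitivity output. A rule chosen after unblinding would be open to challenge.
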